Statistical Analysis Plan (SAP)

Supervised Exercise Therapy using Mobile Health Technology in Patients with
Peripheral Arterial Disease

Principal Investigator	PD Dr. med. [name] Senior physician at the Clinic for Cardiology at the West German Heart and Vascular Center, Essen University Hospital, Essen, Germany
Protocol identification number	18-8355-BO
ClinicalTrials.gov identifier	DERR1-10.2196/13651
Author	Dr. phil. [name] Senior Researcher at the research center for user-centred design, Vorarlberg University of Applied Sciences Dornbirn, Austria
Version	Draft 0.1

Abbreviations

ABI Ankle brachial index

PAD Peripheral arterial disease

QoL Quality of Life

SET Supervised exercise training

1. Introduction

To support supervised exercise training (SET) in patients with peripheral arterial disease (PAD), a smartphone app called TrackPAD will be developed. Aim of this pilot study is to evaluate suitability, feasibility, and the impact on a prognosis relevant outcome measure for patients with PAD, the 6-minutes walking test, by using TrackPAD.

Within this statistical analysis plan (SAP), the study design as well as the statistical analysis will be explained in more detail.

2. Study Design

The pilot study is a two-armed, parallel randomized controlled trial with an intervention period of three months, only including patients with diagnosed and symptomatic PAD. A detailed overview of all inclusion criteria as well as exclusion criteria is given in Table 1.

Participants of the control group will continue to receive therapy without further indication. Participants of the intervention group will receive additional access to the TrackPAD-app, which will be considered as a complement to the patients' current treatment. The TrackPAD-app will be freely accessible to the intervention group. Beside the support during the installation procedure, the app will not require further technical maintenance.

The baseline and follow-up examinations will take place in the outpatient clinic of the vascular department and will include a 6-minutes walk test, measurement of the ankle brachial index (ABI) and a questionnaire package including self-reported physical activity, demographic characteristics and the PADQoL (quality of life) questionnaire.

Table 1. Inclusion and exclusion criteria.

Inclusion criteria	Exclusion criteria
Age \geq 18 years	Wheelchair bound, use of walking aid or walking impairment due to another cause than PAD
Diagnosis of lower extremity PAD based on (and/or): 
• ABI \leq 0.9 in at least one legs• Invasive or non-invasive imaging of stenotic lower extremity artery disease	
• Below or above knee amputation• Acute or critical limb ischemia

 • Endovascular or surgical revascularization of lower extremity artery 	
PAD Fontaine Stage IIa/b	PAD Fontaine Stage I or III / IV
Smartphone with possibility to use TrackPAD: 
 • Android ≥ 5.0 or IOS ≥ 11.0 	
Written informed consent prior to any study procedures, including a specified follow-up evaluation	
 • No German knowledge • Severe cognitive dysfunction
Best-medical treatment in the last 2 months in accordance with standard guidelines	
 • Congestive heart failure with NYHA III-IV symptoms • Active congestive heart failure requiring the initiation or uptitration of diuretic therapy • Angina pectoris with CCS class 3-4 symptoms or myocardial infarction or stroke in the last 3 months • Active arrhythmia requiring the initiation or uptitration of anti-arrhythmic therapy • Severe valve disease

ABI, ankle-brachial index; CCS, Canadian Cardiovascular Society; NYHA, New York Heart Association; PAD, peripheral arterial disease

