2.1. Randomization

All enrolled participants will be randomized by a clinical software (TenAlea) in standard care with or without smartphone-based self-tracking of their physical activity using TrackPAD. The participants will be stratified by their results during the six minutes walking test at baseline (distance less than 362 m, between 362 m and 430 m, more than 430 m).

3. Analysis

For statistical analyses R (version 3.6.0) will be used. In the following, a detailed description of the outcomes, the operationalization and the calculation will be given.

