3.1 Primary Outcomes

The primary outcome is defined as the change in the 6-minutes walking distance and will be measured using a standardized protocol at baseline and after 3 months follow-up. The 6-minutes walking

distance test is objective, well-validated in terms of walking ability that predicts mobility loss and mortality in PAD, and has an excellent test-retest reliability.

To examine differences between the two study groups, a t-test will be performed with a significance level of $p = 0.05$ and a confidence interval (CI) of 95%.

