3.2 Secondary Outcomes

The secondary outcome measures are changes in physical activity and the patient's PAD-related quality of life (QoL), as well as an evaluation of the used app TrackPAD.

Changes in physical activity

Changes in physical activity will be recorded by patient self-report and to analyze differences between the two study groups, a t-test will be performed with a significance level of $p = 0.05$ and a confidence interval (CI) of 95%.

Quality of Life

To measure PAD-related QoL, the PADQoL questionnaire will be used, which is a validated PAD-specific questionnaire. To examine differences in case of QoL, again a t-test will be performed with a significance level of $p = 0.05$ and a confidence interval (CI) of 95%.

Patient centered app evaluation

An evaluation of the TrackPAD app will be measured with the uMars questionnaire (User version of the Mobile Application Rating Scale). Therefore, the evaluation of the TrackPAD app will be measured by analyzing the questionnaire.

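### Does the pilot's feasibility aim need its own outcome, and uMARS a fuller analysis, in this SAP?

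*SAP*

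**What the plan says.** The Introduction gives three aims: "Aim of this pilot study is to evaluate suitability, feasibility, and the impact on a prognosis relevant outcome measure for patients with PAD". Feasibility is the second, and the word does not appear again in the SAP.

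Section 3 (Analysis) opens by saying that "a detailed description of the outcomes, the operationalization and the calculation will be given". Four outcomes follow:

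- Section 3.1, primary: "The primary outcome is defined as the change in the 6-minutes walking distance", compared between arms by t-test.
- Section 3.2: "The secondary outcome measures are changes in physical activity", taken from patient self-report and compared by t-test.
- Section 3.2: PAD-related quality of life from PADQoL, compared by t-test.
- Section 3.2: a patient-centred evaluation of the app by uMARS. The whole analysis is "Therefore, the evaluation of the TrackPAD app will be measured by analyzing the questionnaire".

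Section 2 (Study Design) provides the app to the intervention arm only. It describes a baseline and a follow-up examination, each with "a questionnaire package including self-reported physical activity, demographic characteristics and the PADQoL (quality of life) questionnaire". uMARS is not named there, but the list is introduced as non-exhaustive.

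**The concern.** A pilot that names feasibility as an aim would normally report something like retention, completion of the tests, or continued use of the intervention. None of these is in sections 3.1 or 3.2, although section 3 undertakes to operationalize the outcomes. Three of the four outcomes are comparisons of effect between arms. The fourth is a user rating, which does not show how many patients stayed in the study or went on using the app. The uMARS sentence is also circular: it says the questionnaire will be analysed without saying how.

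If this mattered, one stated aim would end without a planned estimate. The choice of feasibility measure, and the handling of patients who do not return or do not answer, would be left until the data had been seen. The effect estimate for walking distance would not be involved.

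**Working it through.** The SAP gives no sample size, retention rate, app-use rate or feasibility threshold, so there is no figure of its own to reproduce. The check has two parts.

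**1. Aims against outcomes**

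| Item | Stated? | Can it be inferred? |
|---|---|---|
| Outcome labelled as feasibility | No (0 of 4) | Partly: the app evaluation could be read as serving suitability and feasibility together; the SAP ties it to neither |
| uMARS base | No | Yes: only the intervention arm has the app |
| uMARS time point | No | Yes: patients can rate an app only after using it, and the only later visit is at 3 months |
| uMARS score and summary statistic | No | Not from the text; the analyst must choose |
| uMARS non-response | No | Not from the text; the number answering can be reported against the app arm |
| Retention | Not listed | Can be counted from who has a 3-month walk test |

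The unwritten part therefore comes down to the uMARS score, its summary and its non-response, plus a sentence saying what stands for feasibility.

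**2. How much could hang on an unwritten rule?**

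All rates and arm sizes here are assumptions. Let *r* be the proportion of the app arm that returns and *u* the proportion of returners still using the app. Counting non-returners as not using it gives *r* × *u*; leaving them out gives *u*. The gap is *u* − *r* × *u* = *u* × (1 − *r*).

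With *r* = 0.80, *u* = 0.875 and 40 patients:

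- non-returners counted: 28/40 = 70.0% (exact 95% CI 53.5 to 83.4)
- non-returners left out: 28/32 = 87.5% (exact 95% CI 71.0 to 96.5)
- gap: 0.875 × 0.20 = 17.5 points

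Arm size does not enter the formula, so finding the same gap at 20 and 60 patients adds no evidence. The two assumed rates do enter it:

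| *u* | *r* | Gap, *u* × (1 − *r*) |
|---|---|---|
| 0.875 | 0.80 | 17.5 points |
| 0.875 | 0.90 | 8.75 points |
| 0.875 | 0.95 | about 4.4 points |
| 0.875 | 1.00 | 0 |
| 0.50 | 0.80 | 10 points |

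The gap can be anything from 0 to 17.5 points within this range, and it belongs to app use at 3 months, which the SAP does not list as an outcome. It does not measure a defect in what the SAP plans.

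Precision is a separate matter. An observed 80% has an exact 95% CI of 56.3 to 94.3% at 16/20, 64.4 to 90.9% at 32/40 and 67.7 to 89.2% at 48/60. These widths show that a feasibility proportion from small arms would be descriptive. They do not show that its absence does harm.

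**The case for a change.** The strongest case for a change is that the mismatch lies inside this document. The SAP names the aim itself and itself promises operationalization and calculation, so pointing to the protocol does not fully answer it; a citation would have been the least one could expect. The other three outcomes each receive a named test, a significance level and a confidence interval, so the thin uMARS text is not just the general style of the document. Wording would be cheap to add to a plan marked as draft 0.1, and retention needs no new data.

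All of that stands as a description of the text. It does not make a change necessary. Listing retention and uMARS completion would write down what can be counted from the trial's records anyway. A measure of app use would add an outcome that needs either app data, whose availability the SAP does not document, or a new follow-up question. Because no feasibility criterion would be set, the judgement of what counts as feasible would still be made afterwards, which was the harm complained of. Reading uMARS as a measure of suitability alone is also only one interpretation, since the Introduction names the two aims together and section 3.2 has a single app evaluation.

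**Conclusion.** No change follows. The observation is accurate in a narrow form: the SAP does not say which outcome addresses feasibility, and it leaves the uMARS score, summary and non-response unwritten. This is missing detail that an analyst can fill sensibly by reporting how many randomised patients completed the 3-month walk test, and uMARS scores for the app arm at follow-up with the number who answered. Nothing the SAP states is wrong, and the primary result is unaffected.

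The conclusion rests on two readings: that uMARS is given to the app arm at follow-up, which the design makes natural but the text does not state; and that any formal feasibility criteria would be found in the protocol, which was not available to check. No size can be put on the gap from the document itself. The 17.5-point illustration should carry no weight, because it follows entirely from two assumed rates for an outcome that is not planned.

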2.1. Randomization

All enrolled participants will be randomized by a clinical software (TenAlea) in standard care with or without smartphone-based self-tracking of their physical activity using TrackPAD. The participants will be stratified by their results during the six minutes walking test at baseline (distance less than 362 m, between 362 m and 430 m, more than 430 m).

3. Analysis

For statistical analyses R (version 3.6.0) will be used. In the following, a detailed description of the outcomes, the operationalization and the calculation will be given.

3.1 Primary Outcomes

The primary outcome is defined as the change in the 6-minutes walking distance and will be measured using a standardized protocol at baseline and after 3 months follow-up. The 6-minutes walking

distance test is objective, well-validated in terms of walking ability that predicts mobility loss and mortality in PAD, and has an excellent test-retest reliability.

To examine differences between the two study groups, a t-test will be performed with a significance level of $p = 0.05$ and a confidence interval (CI) of 95%.

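### The primary t-test on change ignores baseline walking distance, on which randomisation is stratified, so its confidence interval will usually be wider than it need be.

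*SAP*

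**What the plan says.** SAP section 2 describes a "two-armed, parallel randomized controlled trial with an intervention period of three months". On randomisation, section 2.1 says: "The participants will be stratified by their results during the six minutes walking test at baseline", with three bands ("distance less than 362 m, between 362 m and 430 m, more than 430 m").

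Section 3.1 says: "The primary outcome is defined as the change in the 6-minutes walking distance", measured at baseline and at 3 months. The comparison is then fixed: "To examine differences between the two study groups, a t-test will be performed with a significance level of" 0.05, with a 95% confidence interval. No covariate or stratum term is named there, and no regression, ANCOVA or sensitivity model appears elsewhere in the SAP. Section 3.1 also says that the walking test "has an excellent test-retest reliability", but gives no figure for it.

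**The concern.** The design treats baseline distance as important enough to balance on, and the analysis then makes no use of that balance. A t-test on change is a baseline-adjusted model whose slope has been set to 1 rather than estimated. If the true slope differs from 1, part of the baseline variation stays in the change scores. Stratification keeps most of that variation out of the difference between arms, but the t-test still counts it in its standard error.

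The between-group difference and its interval are the efficacy result of this pilot. An interval that overstates the uncertainty understates what the trial has learned, although the covariate that would correct it has been measured in every randomised patient.

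**Working it through.** The SAP gives no sample size, SD, correlation or power, so there is no planned figure to reproduce.

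**Inputs from the SAP.** The outcome is change in distance, the test is a t-test at 0.05 with a 95% interval, and the stratum cut-points are 362 m and 430 m.

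**Assumptions.**
- N = 40 or 80, 1:1 allocation, permuted blocks of 4 within stratum, two-sided test.
- Baseline to 3-month correlation r = 0.5 to 0.9; ratio k of follow-up SD to baseline SD = 0.9, 1.0 or 1.11.
- Linear relation with baseline, complete follow-up.
- Baseline SD of 78.9 m. This follows if the cut-points are tertiles of a normal distribution: (430 − 362)/(2 × 0.431) = 78.9. The percentages below do not depend on it.

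**Formulas**, in units of the baseline variance, with true slope b = r × k:
- variance of change: 1 + k² − 2rk
- residual variance after fitting baseline: k²(1 − r²)
- difference: (1 − b)², never negative and zero only at b = 1

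The ratio of interval widths, t-test to adjusted model, is the square root of the first variance over the second. With k = 1 it is √(2/(1 + r)).

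**Worked cases.**
- r = 0.8, k = 1: 0.40 against 0.36; √(0.40/0.36) = 1.054, so 5.4% wider.
- r = 0.9, k = 0.9: 0.19 against 0.1539; √1.235 = 1.111, so 11% wider.
- r = 0.9, k = 1.11: b = 0.999, so there is no gain.

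**Simulated 95% interval half-widths**, N = 80, 4000 trials per cell, Welch t-test on change against the model with baseline:

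| r | k = 1.0 | k = 0.9 | k = 1.11 |
|---|---|---|---|
| 0.5 | 35.1 vs 30.3 m (16% wider) | 33.4 vs 27.3 m (22%) | 37.2 vs 33.8 m (10%) |
| 0.7 | 27.1 vs 25.0 m (8%) | 26.0 vs 22.6 m (15%) | 28.9 vs 27.8 m (4%) |
| 0.8 | 22.1 vs 21.0 m (5%) | 21.3 vs 19.0 m (13%) | 23.7 vs 23.3 m (1%) |
| 0.9 | 15.7 vs 15.3 m (3%) | 15.3 vs 13.7 m (11%) | 16.9 vs 17.0 m (0%) |

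The simulated ratios agree with the formula within 0.3 percentage points. At N = 40 with equal SDs the half-widths are 50.4/39.0/31.8/22.5 m against 43.6/35.9/30.2/22.0 m for r = 0.5/0.7/0.8/0.9.

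**Type I error**, N = 80, equal SDs: 2.5/4.0/4.2/4.4% for the t-test and 4.5/5.1/5.1/4.8% for the adjusted model (Monte Carlo error about 0.35 percentage points).

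**Power** at N = 40, equal SDs, for an effect of 2.8 times the t-test's nominal standard error: 80% against 88% at r = 0.5, 79% against 84% at 0.7, and 78% against 79% at 0.9.

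**Cost of estimating the slope.** The variance rises by roughly 1/(N − 5), which is 1/35 = 2.9% at N = 40 and 1/75 = 1.3% at N = 80.

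**A conditional point.** If loss to follow-up depended on baseline and differed by arm, the change-score estimate would shift by (1 − b) times the baseline imbalance among completers. With equal SDs that is 5/3/2/1 m per 10 m of imbalance at r = 0.5/0.7/0.8/0.9. The adjusted estimate would not shift, provided loss depends on nothing beyond baseline and the relation is linear.

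**The case against.** The planned test is not wrong. It is unbiased under randomisation, contradicts nothing in the SAP, and errs on the safe side. This is a pilot that also asks about suitability and feasibility.

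The estimate itself is also hardly noisier than the adjusted one, because stratification has already removed most of the baseline contribution. At N = 80 with equal SDs, the simulated true standard error was 15.85/12.75/10.61/7.78 m for the change score and 15.30/12.46/10.49/7.73 m for the adjusted model at r = 0.5/0.7/0.8/0.9. That is about 3.6%, 2.3% and 1.1% more, and under 1% at r = 0.9. Finally, every input to the size is assumed, and the one hint in the SAP, the good reliability of the walking test, points to a high r and a small gain.

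Most of this stands. It means that the gain comes mainly from an interval and p-value that match the real uncertainty, and only to a small degree from a less variable estimate. It does not remove the gain: the reported interval is still wider and the power lower than they need be. Test-retest reliability is not a 3-month correlation, and a high r alone does not settle the matter, as the 11% excess at r = 0.9 with a 10% smaller follow-up SD shows. The loss scenario has no support in the SAP, which gives no loss rate, and the recommendation does not rest on it.

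**Conclusion.** The point holds, as a matter of efficiency and of an accurate standard error, not of bias or validity. The section 3.1 analysis should be changed. With equal SDs the t-test interval is about 3% to 16% wider than the adjusted one over r = 0.9 to 0.5. The SAP's remark on reliability favours the lower end, about 3% to 5%. Over the SD ratios examined, the excess at r = 0.8 to 0.9 runs from none to about 13%. The gain is therefore usual but not guaranteed: it vanishes when the true slope is 1, and in a very small trial the cost of estimating the slope could cancel it. Confidence in the size is medium, because N, r, both SDs and the block size are assumed.

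**What to change.** In section 3.1, make the primary analysis a linear model of 3-month walking distance on arm, with baseline distance as a continuous covariate. Modelling the change instead gives the identical arm effect. Report the adjusted difference with its 95% interval and keep the t-test on change as a supportive analysis.

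State in advance whether the randomisation stratum is also included. It uses 2 further degrees of freedom and widened the half-width by 0.1 to 0.2 m at N = 80 and 0.3 to 0.6 m at N = 40. The continuous baseline term already carries most of the stratum information.

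The cost is a change of wording in a SAP still marked as a draft and a few lines of R, with no new data or visits. The model assumes a roughly linear relation with baseline. In the least favourable setting run (N = 40, r = 0.9, follow-up SD 11% larger) the half-width was 24.4 m with baseline only and 24.7 m with stratum added, against 24.3 m for the t-test.

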3.2 Secondary Outcomes

The secondary outcome measures are changes in physical activity and the patient's PAD-related quality of life (QoL), as well as an evaluation of the used app TrackPAD.

Changes in physical activity

Changes in physical activity will be recorded by patient self-report and to analyze differences between the two study groups, a t-test will be performed with a significance level of $p = 0.05$ and a confidence interval (CI) of 95%.

Quality of Life

To measure PAD-related QoL, the PADQoL questionnaire will be used, which is a validated PAD-specific questionnaire. To examine differences in case of QoL, again a t-test will be performed with a significance level of $p = 0.05$ and a confidence interval (CI) of 95%.

Patient centered app evaluation

An evaluation of the TrackPAD app will be measured with the uMars questionnaire (User version of the Mobile Application Rating Scale). Therefore, the evaluation of the TrackPAD app will be measured by analyzing the questionnaire.

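### Section 3.2 analyses self-reported activity and PADQoL by unadjusted t-tests; ANCOVA on the baseline score and baseline walking distance would usually be more precise

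*SAP*

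**What the plan says.** SAP section 3.2 opens: "The secondary outcome measures are changes in physical activity and the patient's PAD-related quality of life (QoL"), followed by the app evaluation. For activity it states: "Changes in physical activity will be recorded by patient self-report and to analyze differences between the two study groups, a t-test will be performed" at the 0.05 level with a 95% CI. For quality of life: "To examine differences in case of QoL, again a t-test will be performed with a significance level of" 0.05, again with a 95% CI. Neither sentence names a covariate, and section 3 contains no adjusted or stratified analysis.

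The baseline data will be available. Section 2 describes the visits ("The baseline and follow-up examinations will take place in the outpatient clinic of the vascular department") and includes in them "a questionnaire package including self-reported physical activity, demographic characteristics and the PADQoL (quality of life) questionnaire". Section 2.1 adds: "The participants will be stratified by their results during the six minutes walking test at baseline", in three bands ("distance less than 362 m, between 362 m and 430 m, more than 430 m"). No analysis in section 3 uses that variable as a covariate.

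**The concern.** Activity is explicitly analysed as a change. The quality-of-life sentence does not say whether the tested quantity is a change or the 3-month score. Change is the natural reading, because the opening sentence of 3.2 speaks of changes, the sentence refers back to the test just described, and the primary outcome has the same form ("The primary outcome is defined as the change in the 6-minutes walking distance"). This is loose wording and no more.

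Under that reading the baseline score enters by subtraction. That forces the slope of follow-up on baseline to be 1. With equal variances at the two visits the true slope equals the correlation r, which is below 1, so subtraction over-corrects and adds noise. ANCOVA estimates the slope. The t-tests also leave out the variable on which randomization was stratified.

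At stake is the width of the two confidence intervals the SAP promises. Neither bias nor type I error is in question.

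**Working it through.** **Inputs from the SAP.** Two parallel arms; t-tests at 0.05 with 95% CI; questionnaires at baseline and 3 months; three walking-distance strata. The SAP states no N, SD, correlation or allocation ratio, so it has no figure to reproduce.

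**Assumptions.** 1:1 allocation, two-sided tests, equal score variance at both visits, r from 0.3 to 0.9, total N of 24, 40 or 60.

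**Step 1: large-sample variances**, in units of the score variance:
- t-test on change: 2(1 − r)
- t-test on the 3-month score only: 1
- ANCOVA on the baseline score: 1 − r²

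ANCOVA against change: (1 − r²) / [2(1 − r)] = (1 + r)/2. At r = 0.3, 0.5, 0.7 and 0.9 this is 0.65, 0.75, 0.85 and 0.95, so the variance is 35%, 25%, 15% and 5% lower.

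**Step 2: cost of estimating covariates.** With p covariates, multiply the ANCOVA variance by f = (N − 3)/(N − 3 − p). For p = 2 (baseline score and walking distance, the latter taken as unrelated to the score):
- N = 24: f = 21/19 = 1.105
- N = 40: f = 37/35 = 1.057
- N = 60: f = 57/55 = 1.036

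Variance reduction against the change-score t-test is 1 − f(1 + r)/2. Example, N = 40 and r = 0.5: 1 − 1.057 × 0.75 = 20.7%.

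| Total N | r = 0.3 | r = 0.5 | r = 0.7 | r = 0.9 | break-even r = 2/f − 1 |
|---|---|---|---|---|---|
| 24 | 28% | 17% | 6% | −5% | 0.81 |
| 40 | 31% | 21% | 10% | −0.4% | 0.89 |
| 60 | 33% | 22% | 12% | 1.5% | 0.93 |

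**Step 3: CI width at N = 40.** Square root of the variance ratio, times the ratio of t quantiles on N − 4 = 36 and N − 2 = 38 degrees of freedom: 0.830, 0.892, 0.950 and 1.004 at r = 0.3, 0.5, 0.7 and 0.9.

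**Step 4: the other reading of quality of life (3-month score only), N = 40.** Reduction = 1 − f(1 − r²): 4%, 21% and 46% at r = 0.3, 0.5 and 0.7. Break-even: r² = 1 − 35/37, so r is about 0.23; below that there is a small loss.

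**Step 5: simulation under stratified allocation.** The factor f lets walking distance be imbalanced by chance. Stratification limits that, so f slightly overstates its cost. Simulated trials (N = 40, three strata, permuted blocks of 4 assumed, 12,000 trials per setting, walking distance unrelated to the score) gave variance reductions against change of 31.3%, 23.2% and 11.1% at r = 0.3, 0.5 and 0.7. Null rejection for the change-score t-test was 0.046 to 0.050, so that test is valid.

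**Step 6: what walking distance contributes** (N = 40, r = 0.5, CI width relative to the change-score t-test):
- baseline score alone: 0.879
- plus walking distance, unrelated to the score: 0.883
- plus walking distance, correlated 0.3 with the score: 0.869

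The last figure depends on how the correlation arises. If walking distance relates to the follow-up score only through its baseline value, the ratio is about 0.88.

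**Step 7: power, for illustration.** In a separate simulation (N = 40, 6,000 trials per setting, adjusting for the baseline score and the three bands), power for an assumed 0.8 SD effect at r = 0.5 was about 0.80 to 0.81 with ANCOVA and 0.68 to 0.70 with either t-test.

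**The case against.** The strongest reply is that nothing here is wrong. A pre-specified t-test on change is an unbiased analysis of a randomized comparison, it holds its level, and it already uses the baseline. These are secondary outcomes of a pilot with no power claim attached, and the size of the gain rests on values the SAP does not give. All of that is true, and it is why the point is optional. It does not remove the point: subtracting the baseline is not the same as adjusting for it, and the SAP fixes a method that is usually less precise than one using the same data.

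A second reply is that walking distance is the baseline of neither questionnaire and adds almost nothing. This stands as regards precision (step 6). The reason to include it is that the analysis then reflects the randomization, at very small cost.

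A third reply is that adjusting for the three bands takes two indicators, hence three covariates. By the same formula f is then 37/34 = 1.088 at N = 40 and 21/18 = 1.167 at N = 24, and break-even against change drops to about 0.84 and 0.71. The formula overstates this cost under stratified allocation: in simulation, continuous distance and the three bands gave CI ratios within 0.003 of each other. Either form would do, provided the SAP names it.

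Finally, the same choice matters more for the primary outcome in section 3.1, where walking distance is both the outcome's baseline and the stratifier. That is correct, and it does not make the choice in 3.2 a good one.

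**Conclusion.** The concern holds as a matter of efficiency. ANCOVA is more precise than the planned t-tests over most of the assumed range, by 5% to 17% of CI width at N = 40 for r between 0.7 and 0.3. It is not always better: it loses slightly when r is very high (against change) or very low (against the 3-month score alone), and the range in which it gains narrows in smaller samples. The percentages depend on assumed r, N and equal variances, none of which can be taken from the SAP. The t-tests remain valid, so leaving them unchanged would not invalidate any result.

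**What to change.** In section 3.2, state for PADQoL and for self-reported activity that the 3-month value will be analysed by ANCOVA on arm, the baseline value of the same score and baseline 6-minute walking distance, with the adjusted difference and its 95% CI reported. Say whether walking distance enters as a continuous value or in the three randomization bands. For activity this presumes a roughly continuous score; section 3.2 names no instrument, so that should be confirmed.

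With the baseline score in the model, the arm effect is the same whether the dependent variable is the change or the 3-month value, so the quality-of-life wording no longer matters.

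The cost is a few words in a SAP still marked as a draft and a few lines of R. All the baseline values are already collected. The price in the analysis is two degrees of freedom (three with the bands).

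### Do three unadjusted tests at 0.05 in the primary and secondary analyses leave the trial with an uncontrolled false-positive rate?

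*SAP*

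**What the plan says.** SAP section 3.1 defines one primary outcome, the change in six-minute walking distance from baseline to three months, and fixes its test: "To examine differences between the two study groups, a t-test will be performed with a significance level of" 0.05, with a 95% confidence interval.

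Section 3.2 lists three secondary outcomes.

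- Self-reported physical activity: "to analyze differences between the two study groups, a t-test will be performed with a significance level of" 0.05.
- PAD-related quality of life (PADQoL): "To examine differences in case of QoL, again a t-test will be performed with a significance level of" 0.05.
- App rating by the uMars questionnaire: no test and no level. The text says only that "the evaluation of the TrackPAD app will be measured by analyzing the questionnaire".

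The SAP states no testing order, no multiplicity adjustment and no exploratory label for the two tested secondary outcomes. It does not say whether the tests are one- or two-sided. It also sets no family-wise error rate and no rule by which a secondary result could establish efficacy. Section 1 describes a pilot study of suitability, feasibility and the effect on the six-minute walk.

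**The concern.** The same significance level appears three times with nothing to link the three tests. A reader who treats them as equal routes to a positive result will compute a chance of at least one false finding of about 14%, not 5%.

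The setting adds to the unease. Only the intervention arm receives the app, so patients know their arm. Both tested secondary outcomes are patient-reported, and one of them, physical activity, is the behaviour the app has patients track. If walking distance showed no difference, a significant result on activity or quality of life could be presented as evidence that the app works, at an error rate the reader would wrongly take to be 5%.

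**Working it through.** **Inputs.** The level is 0.05 for walking distance (section 3.1), physical activity and PADQoL (both section 3.2). The uMars rating has no level, so three tests count, two of them secondary. The SAP gives no overall error rate, so there is no figure of its own to reproduce. Sidedness is not stated. Two-sided tests are assumed because each is paired with a 95% interval, so each test has 0.025 in the direction favouring the app. Correlations between the test statistics are assumptions.

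**Step 1: any false significant difference, either direction, independent tests.**

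- Three tests: 1 − 0.95³ = 1 − 0.8574 = 0.1426, or 14.3%.
- Two secondary tests: 1 − 0.95² = 1 − 0.9025 = 0.0975, or 9.75%.

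The arithmetic behind the 14% is therefore right, but it counts results against the app as well as for it.

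**Step 2: false benefit of the app only, independent tests.**

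- One test: 2.5%.
- Three tests: 1 − 0.975³ = 1 − 0.9269 = 0.0731, or 7.3%.
- Two secondary tests: 1 − 0.975² = 1 − 0.9506 = 0.0494, or 4.9%.

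**Step 3: allow for correlation.** Walking distance, activity and quality of life are probably positively correlated. Simulating three equally correlated normal test statistics (4 million draws) gives:

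| Assumed correlation | Any direction, three tests | Benefit only, three tests |
|---|---|---|
| 0 | 14.3% | 7.3% |
| 0.3 | 13.6% | 6.8% |
| 0.5 | 12.5% | 6.3% |
| 0.7 | 10.9% | 5.5% |

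**Step 4: the one-sided variant.** If all three tests were one-sided at 0.05, the chance of a false benefit would be 14.3% under independence and 11.8% at correlation 0.5. So 14% for a false benefit needs both one-sided testing and independence, and the SAP states neither.

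**Step 5: the feared scenario.** With walking distance showing no difference, only the two secondary tests can produce a false claim of benefit. From step 2 that chance is 4.9% under independence. It is about twice the 2.5% for one test in that direction, but it is not well above 5%.

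**Step 6: the primary conclusion.** One outcome is designated primary and is tested once at 0.05. Its type I error is 5% however many secondary tests follow.

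**The case for a change.** The strongest case for the concern is that the SAP itself attached a significance level to each secondary comparison, and section 3 announces a detailed account of the outcomes and calculations. How the three levels relate belongs in such an account. The relative inflation is also real in either direction of counting: 14.3% against 5%, or 7.3% against 2.5%, nearly threefold in both cases. One sentence would settle the matter in a document marked Draft 0.1.

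Part of this stands. The SAP would read better if it stated sidedness and called the two secondary tests exploratory. But that is missing detail. Separating one primary outcome from secondary ones already ranks the endpoints. A family-wise rate over all three tests matters only if any one of them may carry the efficacy claim, and the SAP does not say so. Repeating the same level does not create such a claim.

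Nor is formal control the obvious remedy. Testing the secondary outcomes only after a significant primary result, with Holm across the two, would hold the family-wise error at 0.05 or less. It would also bar every secondary significance claim whenever the primary test is not significant, which is a considerable loss in a pilot. Keeping 95% intervals beside a Holm step at 0.025 could also give an interval that excludes zero for a result declared not significant. Reasonable statisticians differ on this trade-off.

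Reporting bias in unblinded self-reports is a fair worry, but it is a separate one. Adjusting for multiplicity does not reduce it.

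**Conclusion.** The concern does not hold. The SAP does set three between-group t-tests at 0.05 without adjustment, but this contradicts nothing in the document and makes no stated figure wrong. The error rate of the single primary test remains 5%, no family-wise rate is promised, and no rule lets a secondary result prove efficacy.

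The 14.3% is correct only for a false difference in either direction under independence. On the two-sided reading, a false benefit has probability 7.3% over the three tests and 4.9% over the two secondary tests. With positive correlation, the three-test figure falls to between 6.8% and 5.5% at assumed correlations of 0.3 to 0.7. These figures rest on two-sided testing, which the SAP implies by its 95% intervals but does not state. One-sided testing at 0.05 would bring the independent three-test figure back to 14.3%, still without affecting the primary test's 5%. It is also inaccurate that every secondary outcome is tested, because the app rating is not.
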